1. STATISTICAL METHODS PLANNED IN THE PROTOCOL AND DETERMINATION OF SAMPLE SIZE

The objective of this analysis plan is to describe the planned study analyses.

1.1. Statistical and Analytical Plans

1.1.1. Definitions and General Considerations for Data Analysis

- 1. This Statistical Analysis Plan (SAP) is based on Clinical Trial Protocol FluGen-H3N2-V002-V003 dated 18-May-2020 (v8.0).
- 2. All calculations will be performed using SAS statistical software, version 9.4 or later.
- 3. Study Day 1 is the day of randomization and 1st IP administration; Day 29 is the 2nd IP administration.
- 4. Baseline (IP Baseline) is the last observation prior to IP administration, at the data point, not the record level. For example, for laboratory values, individual repeat tests values will be used for baseline when the entire panel may not have been repeated.
- 5. This study is not powered to detect differences in safety or immunogenicity between active and placebo cohorts. The sample size of 250 (200 active subjects and 50 placebo subjects) was chosen empirically based on studies of other vaccines in early stage development.
- 6. There is no plan for test of hypotheses; p-values generated are descriptive only.
- 7. Where possible raw data (not results from calculations) are transferred from external vendors.

1.1.2. Treatment Assignment, Database Lock and Unblinding

1.1.2.1. Randomization

Two hundred-fifty (250) subjects were to be randomized to vaccination or matching placebo (1:1:1:1). Eligible subjects were randomized to receive two administrations (Days 1 and 29) of Sing2016 at three dose levels, Bris10 at one dose level, or placebo The randomization was a permuted block of size 5 with early blocks (sentinel groups) weighted to lower doses of Sing2016. Later blocks were balanced across the 5 treatments (expansion groups). Randomization was local to each site. The randomization was not stratified on any subject baseline characteristics.

1.1.2.2. Database Lock

The database will be locked after the last subject has had the day 209 visit (or terminated the trial early). The Day 209 visit may be by [contact]. Treatment Blinding

ClinDart Data Management (DM) is responsible for supporting ongoing blinded data review and tracking throughout the study. DM will provide SDTM datasets to NRC Statistical Programming. Statistician ([name]) and his designees will have

access to treatment codes throughout the trial and will be responsible for managing data so as not to unblind other team members.

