The reference product (placebo) is a physiological saline suitable for intranasal delivery. The placebo will be provided as a liquid and in single-use vials. The placebo will be drawn into two 1 mL disposable syringes that are fitted with a Teleflex MAD301 sprayer for intranasal delivery. Administration will be as described for the M2SR vaccines.

The placebo is a clear solution whereas the M2SR vaccines are a light yellowish color. The unblinded pharmacy staff will prepare the vaccine and placebo doses, fill delivery devices and apply an opaque label to the device barrel to obscure any coloration of the contents or volume differences and maintain the blind.

Study/Treatment Duration:

All subjects will receive either active vaccine or placebo on Days 1 and 29.

Eligible subjects will be enrolled and receive a first dose on Day 1, be contacted by the site on Day 4 for report of symptoms/AEs (or optionally may attend the clinic if consenting to PBMC collection at select sites) and will attend the clinic on Day 8 for safety follow-up. Subjects will return to the site for a second dose administration on Day 29, be contacted by the site on Day 32 for report of symptoms/AEs and will attend the clinic on Day 36 for safety follow-up. Subjects return to the clinic on Day 57 and then on Day 209 (180 days after the last dose) for the final study follow-up visit. If Day 209 visit cannot be conducted in person, a safety follow-up call will be conducted. Duration of participation for each subject is anticipated to be 7 months.

Sentinel subjects will be treated in three staggered groups of approximately 15. After subjects in all sentinel groups have completed 7 days following first vaccination (Day 8), SRC will review available safety data for sentinel groups 1-3 and the expansion subjects may be enrolled. It is anticipated that a total study length of 8-9 months will be required.

The study will be subject, investigator and sponsor blinded. However, after all sentinel subjects have completed study visits through day 28 after the second dose (Day 57) and/or after all study subjects have completed study visits through 28 days after the second dose administration (Day 57), the study sponsor may be unblinded. Study subjects, blinded investigational site personnel and blinded study monitors will remain blinded until all subjects have completed the study.

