5.6. Blinding

The blind will be maintained during this trial, including use of the following measures:

- (1) All subjects, whether receiving a M2SR vaccine or placebo, will undergo the same procedures, i.e., administration, AE assessment, blood collections, nasal swabs, etc.
- (2) The unblinded pharmacist or designee will prepare doses (active and placebo), fill delivery devices and apply an opaque label to the device barrel to obscure any coloration of the contents.
- (3) The unblinded site staff and unblinded study monitor will agree to maintain the blind by not providing details of the dose (active or placebo) to any blinded clinic staff including the Investigator and to study subjects. Furthermore, the unblinded individuals will be restricted from participating in other study procedures the interpretation of which could be impacted by their unblinded status, such as evaluation of AEs.
- (4) If any blinded investigational site staff learn of treatment assignments, a record of the event will be maintained, and the investigator will be informed. The investigator will consult with FluGen on how to preserve the blind.

With the exception of the unblinded statistician who generates the randomization list, the unblinded pharmacist(s) or their designee(s) who prepare the study product for administration and the unblinded study monitor who may observe the study product preparation and performs IP accountability, all subjects, the Investigator, statistical programmers and all clinical site staff will be blinded to IP treatment (vaccine or placebo). All clinic staff who may be involved in making assessments of safety (including local reactions) will be blinded to treatment. Should a blinded monitor observe study product preparation, precautions must be taken to maintain the blind.

Masking of the IP (vaccine or placebo) will be described in the Pharmacy Manual.

The randomization schedule will be inaccessible to the Investigator or to the blinded study team (monitors and/or FluGen team) during the study. After the Day 209 is complete for all subjects, after database lock, and after reconciliation with pharmacy and site records, the randomization code will be provided to the Study Statistician to enable data analysis by the Sponsor. Data collected at the Day 209 visit will be maintained in a separate follow-up database, and will be unblinded after cleaning and reconciliation, as for the primary database.

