8. STATISTICAL METHODS AND CONSIDERATIONS

8.1. General Considerations

Prior to the analysis of the study data, statistical methods and table shells will be detailed in a Statistical Analysis Plan (SAP) and finalized before database lock.

The final analysis will be done after the last subject has had the day 57 visit and the data base has been locked. The day 209 data will be included as a supplemental analysis.

Statistical analysis will be the responsibility of Northrim Consulting, Inc, using SAS® (SAS Institute Inc., Cary, NC, USA; version 9.4 or higher).

There are primary, secondary and exploratory objectives, endpoints and analyses. Depending upon the result of the primary and secondary analyses, not all exploratory analyses may be done.

Safety and subject disposition analyses will be conducted on the safety analysis set.

Summarization of primary and secondary efficacy endpoints will be done using FAS. These summaries may be repeated using the PP analysis set.

There are no formal tests of hypotheses in this study. Efficacy outcomes are descriptive only.

The data will be summarized in tables listing the number, mean, standard deviation, median, minimum, maximum, standard error (SE) and a 95% CI of subjects for continuous data, or in tables listing count and percentage for categorical data where appropriate. Tables will be presented by IP treatment and overall. Data listing by subject will be provided.

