8.6. Interim Analyses and Data Monitoring

There are no planned interim analyses.

Top line results (grouped by treatment) with no subject-level information may be produced prior to data base lock for sponsor review.

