9.2. Adverse Events (AEs)

Adverse events were to be recorded from informed consent through Day 57 + 28 days. For subjects receiving only one IP administration, follow-up was 28 days. Serious adverse events were recorded through Day 209. During the study treatment period (through Day 57) subjects were asked non-leading questions to determine the occurrence of spontaneously reported (unsolicited) AEs.

Symptoms were collected for the 7 days following each IP administration using Symptom Memory Aids (SMA), with clinical interpretation by the site investigators. A symptom recorded by the subject on the Symptom Memory Aid (SMA) may or may not have been reported as a solicited AE. For clinical interpretation Investigators used the, "Instructions to site investigators on assessing AEs from symptom memory aids (16 October 2019)" as a guideline in assessing whether a symptom was to be reported as an AE. The investigator was responsible for determining the severity and the relationship to IP for these SMA-based (solicited) AEs. There was no reconciliation of the database between the SMA symptoms and adverse event reports.

Symptom Memory Aids were used to facilitate assessment of AEs, as described in Protocol Section 6.2.1.6. Events that were reported in the Symptom Memory Aid were reviewed by the study staff and assessed and recorded as AEs. Investigators were instructed to clinically assess, and record individual symptoms reported by subjects as AEs in order to ensure that all reactogenicity events were captured. However, Protocol Section 9.6 states "Whenever possible, diagnoses should be given when signs and symptoms are due to a common etiology (e.g., cough, runny nose, sneezing, sore throat, and head congestion should be reported as "upper respiratory infection"). After medical review of the AE listing, it appears that some AEs should be grouped as diagnoses. For example, a subject who reported concurrent cough, runny nose, and sneezing assessed by the investigator as unrelated to vaccine should have those symptoms grouped as a syndromic diagnosis (URI), with the severity based on the most severe

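### The protocol and SAP give incompatible rules on who may know treatment and when, and nothing requires the SAP to be final before the sponsor sees data by treatment

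*SAP*

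**What the plan says.** **Rules that restrict access**
- Protocol 3.5.4 names three unblinded roles: the person preparing doses, the unblinded monitor, and the statistician who prepares the randomisation list.
- Protocol 5.6 makes the same exceptions. Otherwise "statistical programmers and all clinical site staff will be blinded to IP treatment (vaccine or placebo"). It closes the schedule to the sponsor's team while the study runs. "After the Day 209 is complete for all subjects, after database lock, and after reconciliation with pharmacy and site records, the randomization code" goes to the Study Statistician.

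**Rules that open access**
- The synopsis (Study/Treatment Duration) calls the study sponsor-blinded, then permits sponsor unblinding "after all sentinel subjects have completed study visits through day 28 after the second dose (Day 57) and/or after all study subjects" have reached that visit.
- The synopsis also allows an early look at partial data. Named team members under a Blinding Plan receive data by group without identifiers, for placebo-versus-active tables. That look may not drive decisions to stop or change the trial.
- SAP 1.1.2.2 gives the statistician and designees "access to treatment codes throughout the trial and will be responsible for managing data so as not to unblind other team members".
- SAP 8.6: "Top line results (grouped by treatment) with no subject-level information may be produced prior to data base lock for sponsor review".

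**When the SAP must be final**
- Protocol 8.1 asks for the methods ahead of the analysis; they "will be detailed in a Statistical Analysis Plan (SAP) and finalized before database lock". The synopsis gives the same lock deadline.
- SAP 1.1.2.2 places lock after the last Day 209 visit. Protocol 8.1 instead describes a final analysis after Day 57 and a lock, with Day 209 as a supplement.

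**Rules in the SAP of 28 July 2020 that differ from or add to the protocol**
- Section 2 drops the Full Analysis and Per-protocol Sets and introduces an Evaluable Set, which requires both doses. Section 9.2.1 uses it for the symptom memory-aid tables.
- Section 9.2 adds a grouping of symptoms as upper respiratory infection: "After medical review of the AE listing, it appears that some AEs should be grouped as diagnoses".

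**The concern.** A reader cannot tell from these documents who was meant to know treatment assignment, or from what date. The one firm deadline for the SAP is database lock, and access to treatment information can come well before lock. Analysis sets, groupings and summaries could be chosen by people who had already seen results by arm.

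The Evaluable Set shows what is at stake. Protocol 8.1 puts safety analyses on the Safety Set, yet the SAP tabulates memory-aid reactogenicity only in subjects who received both doses. Someone who stopped after dose 1, including because of a reaction, is missing even from the dose 1 table. In an arm of about 40 (the enrolment reported in SAP section 12), each subject is 1/40 = 2.5 percentage points. SAP section 12, which lists changes to the planned analyses, mentions neither this replacement nor the grouping rule, and does not say whether either was decided blind.

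**Working it through.** The plan states no figure to reproduce here. The check sets the access rules side by side and then uses Table 2 to size the windows.

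**Access rules**

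| Role | Protocol 3.5.4 / 5.6 | Synopsis / SAP |
|---|---|---|
| List-generating statistician | Holds codes | SAP statistician holds codes throughout; not stated whether this is the same person |
| Statistician's designees | No exception made | Hold codes throughout (SAP 1.1.2.2) |
| Statistical programmers | Blinded | Not excluded from the designees |
| Study Statistician | Code after Day 209, lock and reconciliation | As for the SAP statistician, if the same person |
| Sponsor | No access during the study | May be unblinded after sentinel Day 57 (synopsis); results by treatment before lock (SAP 8.6) |

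The sponsor and designee rows conflict directly. The early-look clause limits the tables to placebo versus active, which SAP 8.6 does not.

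**Calendar**

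Inputs from Table 2: sentinel group 3 has dose 2 in Week 9. The first expansion wave (5 × 21 = 105 subjects) has dose 2 in Week 12 in the synopsis and Week 11 in the body. The second wave (5 × 20 = 100) has dose 2 in Week 14 in both. Day 57 is dose 2 + 28 days and Day 209 is dose 2 + 180 days. Week w starts on calendar day 7(w − 1) + 1.

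- Sentinel group 3, dose 2: 7 × 8 + 1 = day 57. Its Day 57 visit: 57 + 28 = day 85, in Week 13.
- Second wave, dose 2: 7 × 13 + 1 = day 92. Gap from the sentinel trigger: 92 − 85 = 7 days. The ±7-day window on the Day 57 visit makes this 0 to 14 days.
- First-wave Day 57 falls in Week 15 or 16 and second-wave Day 57 in Week 18. All 105 + 100 = 205 planned expansion subjects are therefore still in adverse-event collection when sponsor unblinding becomes allowed.
- Last Day 57: 92 + 28 = day 120. Last Day 209: 92 + 180 = day 272.

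**Window between permitted unblinding and the SAP deadline**

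- Lock after Day 209 (SAP): 272 − 85 = 187 days from the sentinel trigger. With the ±7 and ±14-day visit windows this is 166 to 208 days. From the all-subject Day 57 trigger it is 272 − 120 = 152 days.
- Lock at Day 57 (protocol 8.1): 120 − 85 = 35 days from the sentinel trigger, and none from the all-subject trigger.

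The sentinel trigger precedes the SAP deadline under either reading of lock.

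**The case against.** There is a substantial case on the other side.

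- **A statistician holding codes is not in itself a breach.** Protocol 3.5.4 and 5.6 exempt the list generator, and the SAP makes code-holders responsible for protecting the blind. This stands. The conflict lies with the designees, the programmers, the release rule for the Study Statistician and the sponsor clause.
- **Safeguards exist.** Sites, subjects and blinded monitors stay blinded to the end. The early look is controlled by a Blinding Plan, which was not available here. Protocol 8.1 wants methods set before analysis. These count, but none bars people who know treatment from setting analysis rules. The early-look restriction covers changes to the trial, not to the analysis.
- **The 152 and 187 days depend on the SAP's later lock.** This is correct; under a Day 57 lock the window is 35 days. The 7-day gap is also within one visit window, and 205 is a planned number. With about 40 per arm and all sentinels enrolled, expansion would be about 5 × (40 − 9) = 155.
- **The study is descriptive.** There are no formal tests, so no error rate is at risk.

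A reader might go further and make three inferences that the documents do not support:

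- **That the primary related-event counts are biased.** The respiratory grouping is a secondary presentation, limited to events that blinded investigators had already judged unrelated. It cannot change related-event counts. Those counts use the Safety Set, whose definition is essentially the same in both documents.
- **That stopping enrolment at about 40 per arm reflects unblinding.** SAP section 12 gives seasonal influenza as the reason. Planned first doses end in Week 9 or 10, before the Week 13 trigger.
- **That the rules were in fact set with treatment known.** Nothing shows this.

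**Conclusion.** The blinding rules contradict each other and should be reconciled. The documents allow the sponsor to be unblinded, or to see results by arm, before the SAP has to be final. On planned dates the sentinel trigger comes 35 days before all subjects reach Day 57, the earliest point for a Day 57 lock. It comes about 187 days before the last Day 209 visit, if lock follows that visit as the SAP says. This rests on the Table 2 calendar; the actual dates of unblinding, data release and lock are not given.

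The conclusion is about what was possible. The exposed results are mainly the memory-aid reactogenicity tables, through the Evaluable Set. They bear on tolerability, which is part of the primary objective, but they are not the related adverse-event counts. If every rule was decided blind, one dated sentence would settle the matter; neither document contains it.

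**What to change.** 1. Write one access rule and use it in the synopsis (sponsor unblinding and early review), protocol 3.5.4 and 5.6, and SAP 1.1.2.2 and 8.6. Name the roles that hold codes, and say whether the SAP statistician is the list generator and who the designees are.
2. Require the SAP, including analysis sets and event groupings, to be signed before any treatment-grouped or unblinded data go to the sponsor or to those who write the SAP.
3. Limit any earlier sponsor review to the placebo-versus-active tables that the synopsis already describes under the Blinding Plan.
4. In SAP section 12, give the date when treatment-grouped data were first released and the roles that received them. List the replacement of the protocol's analysis sets and the respiratory grouping as changes, and label any rule set after that date post hoc.
5. Show the memory-aid reactogenicity tables on the Safety Set beside the Evaluable Set.

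The cost is wording, a dated access record and one repeated set of tables; no new data are needed. The downsides are small: the sponsor sees by-arm results later, and some analyses may carry a post hoc label. Removing sentinel-stage sponsor unblinding altogether would go further, but it trades against programme planning and is not needed if items 2 and 3 are in place.

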2. ANALYSIS POPULATIONS

Three populations will be formed: Randomized Set, Safety Set, and the Evaluable Set.

2.1.1.1. Randomized Set (RS) Population

The RS consists of all subjects randomized to the study.

2.1.1.2. Safety Set (SS) Population

The SS Population will consist of all randomized subjects who receive at least one IP administration.

2.1.1.3. Evaluable Set (EVAL) Population

The Evaluable Set will consist of all randomized subjects who receive both administrations of IP.

3. SUBJECT DISPOSITION (RS)

Subjects will be accounted for as follows:

- 1. N(%) of subjects randomized
- 2. N(%) of subjects who received first IP administration (SS)
- 3. N(%) of subjects who received second IP administration (EVAL)
- 4. N(%) of subjects who complete Treatment Period (Day 57)
- 5. N(%) of subjects who complete Follow-up (Day 209).

Reason for exclusion from safety and evaluable sets will be tabulated.

Screen failures were not collected in the database.

4. PROTOCOL DEVIATIONS (SS)

N(%) of protocol deviations will be displayed by treatment and deviation type (missed visit, prohibited medication, missed procedure, procedure out of window, etc.). Protocol deviations resulting in subject exclusion from the evaluable set will be reported in the clinical study report (CSR).

5. DEMOGRAPHIC AND BASELINE CHARACTERISTICS (SS)

N (%) of subject will be displayed by treatment for gender, race, age, ethnicity, height, weight, BMI, and Investigational Site. Summary statistics (N, Mean, SD, Median, Min, Max) will be displayed for continuous variables. N(%) will be displayed for categorical variables.

6. MEDICAL HISTORY (SAFETY SET)

Significant medical histories will be listed with condition and start and end dates. Medical histories with no end date will be reported as continuing.

7. CONCOMITANT MEDICATIONS/THERAPIES (SS)

Medications collected from informed consent and will be coded according to Who Drug (WHODrug Sep2019) and presented by therapeutic main group (ATC2) and preferred term. Concomitant medications will include all those taken during the study (Day 1 – Day 57). Medications starting after informed consent and stopped prior to Day 1 will be included in the listings, but not in the concomitant medication summary.

8. EFFICACY ANALYSIS

8.1. Primary

The primary objective of this study is safety. Efficacy is not a primary objective.

8.2. Secondary

Immunogenicity data sources include influenza-specific serum antibody responses (MN, HAI, ELLA) and mucosal IgA antibody responses as listed below.

External Vendor-supplied data to be integrated into the clinical database.

Vendor Name	Specimen Material Type	ISTESTCD (Test Virus)	ISSCAT (Assay Type)	Comment
Southern Research	SERUM	BRIS	MN	No LLOQ, lowest values reported = 5.
Southern Research	SERUM	SING	MN	No LLOQ, lowest values reported = 5.
Viroclinics	SERUM	BELG	MN	
Viroclinics	SERUM	BRIS	HAI	•

Viroclinics	SERUM	H6N2	ELLA	
Viroclinics	SERUM	KANS	HAI	
Viroclinics	SERUM	KANS	MN	
Viroclinics	SERUM	Hong Kong	НАІ	
Viroclinics	SERUM	Hong Kong	MN	
Viroclinics	SERUM	SING	HAI	
Viroclinics	SERUM	SWTZ	HAI	
Viroclinics	SERUM	SWTZ	MN	
		,	,	
VisMederi	NASAL MUCUS	BRIS	SIgA	LLOQ=3; set to 1.5. At the replicate level.
VisMederi	NASAL MUCUS	SING	SIgA	LLOQ=3; set to 1.5. At the replicate level.
VisMederi	NASAL MUCUS	TOTIGA	SIgA	No LLOQ.
VisMederi	NASAL MUCUS	BRISC= BRIS/TOTIGA	SIgA	BRIS to be corrected for TOTIGA. If TOTIGA <1 then BRISC= missing, otherwise BRISC=BRIS/TOTALIGA.
VisMederi	NASAL MUCUS	SINGC= SING/TOTIGA	SIgA	SING to be corrected for TOTIGA. If TOTIGA <1 then SINGC= missing, otherwise SINGC=SING/TOTIGA

Serum antibody response (influenza-specific HAI, MN, and ELLA results) after one and after both administrations of M2SR vaccine will be summarized by treatment comparisons of GMT, GMFR, seroprotection, and seroconversion (2-fold and 4-fold).

GMTs will be summarized at Days 1, 29, and 57; GMFR will be summarized by Day 29/Day 1, Day 57/Day 1, and Day 57/Day 29. Ln-transformed GMT and the Intransformed GMFR ratios will be analyzed using ANCOVA with baseline (Day 1) values as a covariate. [Note: GMFR Day 57/Day29 is modelled with Day 1 baseline covariate.]

Conversion rates categorized as >=2-fold and >= 4-fold values will be reported for Days 29 and 57. Pairwise comparisons of conversion counts (%) will be done using Fishers Exact Tests.

Seroprotection rates at Days 1, 29 and 57 will be presented for the hemagglutination inhibition (HAI) assay only. Pairwise comparisons of seroprotection counts (%) will be done using Fishers Exact Tests.

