2.2.2. Secondary Endpoints

The secondary endpoints are:

1. The number and percentage of study participants who after one or two doses of Bris10 M2SR or placebo demonstrate:
 - i. Influenza-specific serum antibody responses measured at specified time points;
 - ii. Influenza-specific mucosal immunoglobulin A (IgA) antibody responses measured at specified time points;
 - iii. Influenza-specific cellular immune responses measured by cytokine enzyme-linked immunospot (ELISPOT) at specified time points.
2. The number and percentage of study participants who after one or two doses of Sing2016 M2SR or placebo demonstrate:
 - i. Influenza-specific serum antibody responses measured at specified time points;
 - ii. Influenza-specific mucosal IgA antibody responses measured at specified time points;
 - iii. Influenza-specific cellular immune responses measured by ELISPOT at specified sampling time points.
3. Vaccine virus shedding evaluated by influenza A-specific qPCR on day 7 post IP administration.

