8.2.1. Secretory IgA Immune Response and Viral Shedding from Nasal Swab

Summary statistics for secretory IgA immune response (influenza A-specific and total IgA ELISA) at Days 1 (baseline), 29, and 57 post IP administration will be provided.

Summary statistics for viral shedding (influenza A-specific q-PCR) at Screening, Days 1 and 8, will be provided.

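### The SAP does not deliver the protocol's percentage of mucosal IgA responders, and its total-IgA correction treats values substituted below the LLOQ as if they were measured

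*SAP*

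**What the plan says.** Protocol 2.2.2 frames the secondary immunogenicity endpoints as responder counts. For Sing2016 the stem is "The number and percentage of study participants who after one or two doses of Sing2016 M2SR or placebo demonstrate", and one item under it is "Influenza-specific mucosal IgA antibody responses measured at specified time points". The Bris10 endpoint has the same form.

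For the nasal swabs, the vendor table in SAP 8.2 gives this rule for specific IgA to each strain: "LLOQ=3; set to 1.5. At the replicate level". Corrected variables follow: "If TOTIGA <1 then SINGC= missing, otherwise SINGC=SING/TOTIGA" for Sing2016 and "If TOTIGA <1 then BRISC= missing, otherwise BRISC=BRIS/TOTALIGA" for Bris10 (TOTALIGA is evidently the same variable as TOTIGA). The only exception is total IgA below 1.

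The planned output in SAP 8.2.1 is: "Summary statistics for secretory IgA immune response (influenza A-specific and total IgA ELISA) at Days 1 (baseline), 29, and 57 post IP administration". Fold rises and 2-fold and 4-fold conversion rates appear in SAP 8.2 after a paragraph that opens "Serum antibody response (influenza-specific HAI, MN, and ELLA results) after one and after both administrations of M2SR vaccine will be summarized".

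SAP section 12 lists the enrolment stop at about 40 per group, the telephone visits at Day 209, and the ELISPOT and shedding data not available at lock. It does not mention mucosal IgA.

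**The concern.** There are two linked problems.

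- **Endpoint.** The protocol promises a percentage of participants. A percentage needs a definition of response, and neither document gives one for mucosal IgA. If the SAP is followed as written, this endpoint goes unreported and no change is recorded.
- **Derivation.** Dividing by total IgA to allow for swab yield is reasonable for a measured value. When every replicate has been replaced by 1.5, the numerator is a constant and the corrected value is only the reciprocal of total IgA, scaled. It is then handled as if it were a measured ratio.

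The two are linked because a responder percentage added later on the present derivation could count a change in swab yield as an antibody response.

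**Working it through.** **Inputs.** From SAP 8.2: LLOQ 3, substituted value 1.5, corrected value = specific IgA / TOTIGA, missing if TOTIGA < 1. The documents give no units, range or spread for total IgA, and no share of swabs below the LLOQ.

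**The plan's own figure.** LLOQ/2 = 3/2 = 1.5, which reproduces the substituted value.

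**Level below the LLOQ.** With all replicates substituted, the corrected value is 1.5/TOTIGA. TOTIGA of 1, 2, 5, 10 and 100 gives 1.5, 0.75, 0.30, 0.15 and 0.015. The numerator does not vary across these.

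**When ranks reverse.** Take a swab below the LLOQ with total IgA T1 and a quantifiable swab with specific IgA S and total IgA T2. The first scores higher when 1.5/T1 > S/T2, that is, when T2/T1 > S/1.5. The last column is an illustration only: it assumes independent lognormal total IgA with SD of ln(TOTIGA) = s between 0.3 and 1.0, so that P = 1 − Φ(ln(S/1.5)/(s√2)).

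| S | T2/T1 must exceed | Chance of reversal, s = 0.3 to 1.0 (assumed) |
|---|---|---|
| 3 | 3/1.5 = 2 | 5% to 31% |
| 6 | 6/1.5 = 4 | 0.1% to 16% |
| 12 | 12/1.5 = 8 | about 0% to 7% |
| 30 | 30/1.5 = 20 | about 0% to 2% |

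**Fold change, if one is computed.** For a subject below the LLOQ at both visits, (1.5/TOTIGA post) / (1.5/TOTIGA Day 1) = TOTIGA(Day 1)/TOTIGA(post). If total IgA halves, the result reads as a 2-fold rise; if it doubles, as a 2-fold fall.

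**Mixed replicates.** Substitution is per replicate, and the SAP does not say how replicates are combined. If they are averaged, one replicate below the LLOQ and one at 4 give (1.5 + 4)/2 = 2.75, which is below the LLOQ but not equal to 1.5.

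**Endpoint against output.** Protocol 2.2.2 calls for a count and percentage with a mucosal IgA response. SAP 8.2.1 gives summary statistics, and no text in either document sets a threshold. Protocol 8.3.4 also speaks of descriptive statistics for mucosal antibody. That does not remove the endpoint, since a count and percentage is itself descriptive.

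**The case against.** The strongest reply concerns what is actually reported. SAP 8.2.1 names specific and total IgA and does not say whether the corrected ratios are summarised. If conversion rates are for serum only, no IgA fold rise is planned and the fold-change problem touches no table. If the conversion sentence, which does not repeat the word serum, is read to include IgA, then a responder percentage does exist.

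Much of this stands. The fold-change result is conditional, and I state it so. But neither reading clears the plan. On the serum-only reading, which the separate IgA section supports, the endpoint is missing. On the wider reading, the percentage would be computed with no rule for values below the LLOQ. The corrected variables are derived in the section on secondary immunogenicity data, so their use appears intended, and the problem with levels needs no fold rise.

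Three further points are fair. A value below the LLOQ is not evidence of no antibody: it bounds the ratio between 0 and 3/TOTIGA, and 1.5/TOTIGA is the midpoint. The rule already drops swabs with total IgA below 1. The SAP tests no formal hypotheses.

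A reader might infer three stronger things that the documents do not support:

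- **That swabs below the LLOQ routinely outscore strong positives.** The rule permits 1.5/1 = 1.5 against 30/100 = 0.30, but that pairing needs a 100-fold difference in total IgA, with one swab exactly at the exclusion limit.
- **That a known share of such subjects would be reported as responders.** No spread of total IgA is given, and no IgA fold rise is clearly planned.
- **That the rule favours vaccine over placebo.** If total IgA has the same distribution at both visits, swab-yield noise creates falls as readily as rises, in every arm. A bias would need vaccination to change total IgA, and nothing in the documents shows that.

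**Conclusion.** The concern holds in this limited form. Following the SAP leaves a stated secondary endpoint unreported without a recorded change; this rests on the text alone, with the conversion rates read as serum only. The corrected IgA values also let swab yield pass for antibody level when the numerator is substituted. That follows from the SAP's own rule, for swabs whose replicates are all below the LLOQ, and it affects results wherever the corrected values are used. The effect is concentrated near the LLOQ, where a 2-fold difference in total IgA is enough; at ten times the LLOQ a 20-fold difference is needed. How often this occurs cannot be derived from the documents, and the percentages in the table depend on an assumed spread. What is shown is added noise, not bias between arms. It is worth correcting before the analysis, but the endpoint is secondary and descriptive and the primary safety evaluation does not depend on it.

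**What to change.** 1. **Summaries.** State in SAP 8.2.1 that SINGC and BRISC are summarised. Say how replicates are combined, and treat a swab as below the LLOQ when its combined specific IgA is below 3. Flag those swabs, report N (%) quantifiable by arm and visit beside the geometric means, and handle values below the LLOQ as left-censored at 3/TOTIGA, for example with a censored lognormal likelihood.
2. **Responders.** Report N (%) mucosal responders by arm at Days 29 and 57. A responder has post-dose specific IgA at or above the LLOQ and a rise of at least 2-fold (also shown at 4-fold) in the corrected value over Day 1. The cut-offs are borrowed from the SAP's serum conversion rates and are a proposal. When Day 1 is below the LLOQ, use 3/TOTIGA as the Day 1 value, so that the rise is a lower bound. A subject below the LLOQ post-dose is a non-responder.
3. **Otherwise**, record in SAP section 12 that the protocol's percentage endpoint for mucosal IgA is not reported.

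This needs SAP wording, a derivation change and added table rows, with no new samples or assays. The cost is a slightly more complex summary and a conservative rule for a Day 1 value below the LLOQ. For example, with TOTIGA 10 at both visits and post-dose specific IgA of 4, the present rule gives 0.4/0.15 = 2.67, while the lower bound is 0.4/0.3 = 1.33 and the subject is not counted. At unchanged total IgA, such a subject needs a post-dose value of at least 6 for 2-fold (2 × 3) or 12 for 4-fold (4 × 3).
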